##### **11.3.2.1 IOP**

If both eyes qualify for study inclusion, analyses will be provided for the worse eye at baseline. If both study eyes are the same at baseline, then data for only the right eye will be analyzed.

The primary efficacy variable is percent reduction from baseline IOP.

#### **11.3.3 Safety Analyses**

Safety data will be summarized for the Safety population.

##### **11.3.3.1 Adverse Events**

All treatment-emergent AEs/SAEs will be summarized with frequency distributions by treatment group, system organ class, and preferred term using version 21.1 of the Medical Dictionary for Regulatory Activities (MedDRA) as well as by ocular versus non-ocular. Specific AEs/SAEs occurring with a frequency of 5% or more will be summarized in a separate listing.

Descriptive statistics will also be provided as data summaries.

**11.3.3.2 Other Safety Assessments**

Other safety variables (as recorded on the eCRF) will be either summarized or listed based on the frequency.

**11.3.4 Other Assessments**

[REDACTED]

- [REDACTED]
- [REDACTED]
- [REDACTED]
- [REDACTED]
- [REDACTED]
- [REDACTED]
- [REDACTED]

**11.4 Interim Analysis**

No interim analyses are planned.

**12.0 ADMINISTRATIVE CONSIDERATIONS**

**12.1 Protection of Human Subjects**

**12.1.1 Informed Consent Regulations**

Written informed consent is to be obtained from each subject prior to enrollment into the study, and/or from the subject's legally authorized representative.

**12.1.2 Ethics Committee and Independent Review Board Regulations**

This study is to be conducted in accordance with Ethics Committee/IRB regulations. The investigator must obtain approval from a properly constituted Ethics Committee/IRB prior to initiating the study and re-approval or review at least annually. Aerie is to be notified immediately if the responsible Ethics Committee/IRB has been disqualified or if proceedings leading to disqualification have begun. Copies of all Ethics Committee/IRB correspondence with the investigator should be provided to Aerie.

**12.1.3 Good Clinical Practice Regulations**

This protocol is to be conducted in accordance with the applicable Good Clinical Practice regulations and guidelines.

**12.2 Changes to Protocol**

The investigator should not implement any deviation from or changes to the protocol without approval by Aerie and prior review and documented approval/favorable opinion from the Ethics Committee/IRB of a protocol amendment, except where necessary to eliminate immediate hazards to study subjects, or when the changes involve only logistical or administrative aspects of the study (eg, change of telephone numbers, etc.).

### **12.3 Quality Control and Assurance**

The progress of this study will be monitored by on-site, written, and telephone communications between personnel at the investigator's site and the study monitor. The investigator will allow the sponsor or designee to inspect all documents pertinent to the study, including but not limited to: CRFs, subject records (source documents), signed informed consents, records of study medication receipt, storage and disposition and regulatory files related to the study.

### **12.4 Subject Confidentiality**

Written authorization is to be obtained from each subject prior to enrollment into the study, and/or from the subject's legally authorized representative in accordance with the applicable privacy requirements (eg, HIPAA).

### **12.5 Required Study Documents**

The investigator will maintain documentation demonstrating Ethics Committee/IRB approval of the study protocol and informed consent at his/her study site.

The investigator is responsible for ensuring that data are properly recorded on each subject's CRFs and related documents. The CRFs are to be submitted in a timely manner and according to an Aerie-specified schedule.

### **12.6 Record Retention**

The investigator must maintain records related to this study for a minimum of 3 years after study completion.

APPENDIX 1: [REDACTED] QUESTIONNAIRE

Administered by the investigator (or designee)

Subject I.D. \_\_\_\_\_

Study Site: \_\_\_\_\_

Date Completed: \_\_\_\_/\_\_\_\_/\_\_\_\_  
Month/Day/Year

- 1. [REDACTED]
  - [REDACTED]
  - [REDACTED]
- [REDACTED]
  - [REDACTED]
  - [REDACTED]
  - [REDACTED]
  - [REDACTED]
  - [REDACTED]
- [REDACTED]
  - [REDACTED]
  - [REDACTED]
  - [REDACTED]
  - [REDACTED]
  - [REDACTED]
- [REDACTED]
  - [REDACTED]
  - [REDACTED]
  - [REDACTED]
  - [REDACTED]
- [REDACTED]
  - [REDACTED]
  - [REDACTED]
  - [REDACTED]
  - [REDACTED]
- [REDACTED]
  - [REDACTED]
  - [REDACTED]
  - [REDACTED]
- [REDACTED]
  - [REDACTED]
  - [REDACTED]
- [REDACTED]
  - [REDACTED]
  - [REDACTED]
  - [REDACTED]
  - [REDACTED]

APPENDIX 2: [REDACTED] QUESTIONNAIRE

Subject I.D. \_\_\_\_\_  
Study Site: \_\_\_\_\_  
Date Completed: \_\_\_\_/\_\_\_\_/\_\_\_\_  
Month/Day/Year

[REDACTED]  
[REDACTED]  
[REDACTED]

[REDACTED]  
[REDACTED]  
[REDACTED]

[REDACTED]  
[REDACTED]  
[REDACTED]

[REDACTED]  
[REDACTED]  
[REDACTED]  
[REDACTED]  
[REDACTED]  
[REDACTED]

[REDACTED]  
[REDACTED]  
[REDACTED]

**APPENDIX 3: STUDY MEDICATION PACKAGE INSERT**

Package Insert for Rhopressa (netarsudil ophthalmic solution) 0.02% will be supplied separately to each study site.

**APPENDIX 4: SCHEDULE OF VISITS/PROCEDURES**

Procedure	Visit number Visit Window	1 Baseline (Day 0)	2 Follow-Up (Week 6) ±7 days	3 Final (Week 12) ±7 days
Informed consent & HIPAA authorization		X		
Demographics		X		
Subject eligibility (inclusion/exclusion) 		X		
Urine pregnancy test 		(X)		
Medical and IOP history		X		
Prior and concomitant medications and/or procedures review/changes		X	X	X
BCVA 		X	X	X
Biomicroscopy		X	X	X
IOP measurement 		X	X	X
Blood pressure measurement 		X	X	X
Pachymetry		X		
AE assessment			X	X
██████████ Questionnaire 				X
██████████ Questionnaire 				X
Dispense study medication bottles		X	X	
Collect used/unused study medication bottles			X	X

X = required, (X) = only if needed.

1. Women of childbearing potential must be willing to practice effective contraception for the duration of this study.
2. Female subjects only (if applicable).
3. Assessed using Snellen logarithmic visual acuity chart.
4. Assessed using Goldmann applanation tonometer affixed to a slit lamp. IOP must be measured following completion of the biomicroscopic examination.
5. Measured after the subject has been at rest in a sitting position for 5 minutes.
6. To be administered by the investigator (or designee).
7. To be completed by the investigator (or designee).

**APPENDIX 5: EXAMINATION PROCEDURES**

**1. Best Corrected Visual Acuity**

At all study visits, BCVA will be assessed in both eyes of each subject using a logarithmic visual acuity chart (Snellen or equivalent) at a distance of 12 feet.

Ensure subject is seated in a position whereby his/her eyes are 12 feet from the chart, which is hung on the wall at eye level. Mark a spot on the floor with a piece of tape to ensure subjects are seated in the exact same position every time they take the test. Also ensure subject is fitted with appropriate lenses as to provide “best correction” each time he/she takes the test. In order to standardize the conditions of the test as much as possible, all visual acuity testing should be performed in the same room under the same lighting conditions for every subject.

Perform the test on the right eye first. Ask the subject to read each letter, line by line, left to right beginning with line #1 on the top of the chart. Subjects should be told that the chart contains only letters, not numbers. If the subject reads a number, he/she should be instructed that the chart only contains letters and for him/her to “try again.” Subjects should be asked to read the letters slowly as to achieve best identification of each letter. There is no time limit for this test. Subjects are not to proceed to the next letter (or line) until they have given a finite answer.

If a subject changes a response (eg, that should be a “C” not an “O”) before he/she has read the next letter, the change will be accepted. If the subject attempts to change a response after reading the next letter in the series, the change will not be accepted.

When the letters become difficult to read or if the subject identifies a letter as 1 of 2 letters, he/she should be instructed to choose 1 letter and, if necessary, to guess. The examiner should consider the lowest line read with no more than 1 mistake as the extent of a subject’s visual acuity. This visual acuity should then be recorded (in Snellen equivalent units, eg, 20/80) on the appropriate CRF.

Repeat for the left eye.

**2. Biomicroscopy**

Any findings from the gross examination will be recorded in this section on the CRF. Slit lamp biomicroscopy without fluorescein and without dilation of the pupil will be performed during the study (fluorescein may be used if corneal erosion is suspected). Observations for the slit lamp biomicroscopy examination will be graded as follows:

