**Cornea**

*Edema*

Rating	Score	Description
None	0	No edema
Trace	+0.5	Localized, minimal (trace) epithelial haze
Mild	+1	Dull glass appearance of epithelium that may include fine localized microcystic changes
Moderate	+2	Dull glass appearance of epithelium with large number of cystic changes with or without stromal edema
Severe	+3	Epithelial bullae and/or stromal edema, localized or diffuse, with or without stromal striae

*Staining/Erosion*

Rating	Score	Description
None	0	No erosion
Trace	+0.5	Minimal fluorescein staining confined to small focus
Mild	+1	Slight fluorescein staining confined to small focus
Moderate	+2	Regionally dense fluorescein staining (1 mm or greater in diameter) with underlying structure moderately visible
Severe	+3	Marked fluorescein staining or epithelial loss

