#### Test Procedure:

1. With the subject seated, both he/she and the slit lamp should be adjusted so that the subject's head is firmly positioned on the chin rest and against the forehead rest without leaning forward or straining.
2. Look through the binocular viewer of the slit lamp at low power making sure the tension knob is pre-set to the low-pressure value (4-6 mmHg).
3. Follow the image of the fluorescein-stained semicircles while rotating the tension knob until the inner borders of the fluorescein rings touch each other at the midpoint of their pulsation in response to the cardiac cycle.
4. When this image is reached, remove your fingers from the tension knob and record the IOP reading along with the time of day in the CRF.

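### Corneal staining grades 0.5 to 2 need fluorescein, but dye is used only when erosion is suspected and no not-assessed level is listed, so low-grade staining may be under-recorded

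*Protocol*

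**What the plan says.** **Method.** Protocol Appendix 5, item 2 (Biomicroscopy): "Slit lamp biomicroscopy without fluorescein and without dilation of the pupil will be performed during the study". A parenthesis in the same sentence adds that "fluorescein may be used if corneal erosion is suspected".

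**Scale.** In the Staining/Erosion table under Cornea, in the same appendix, the lowest positive grade (0.5) is worded as "Minimal fluorescein staining confined to small focus". The next two grades, 1 and 2, describe progressively more of the same sign and are again defined by the dye alone. Only the top grade (3) offers another route: "Marked fluorescein staining or epithelial loss". Grade 0 is described as no erosion, without mention of dye.

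**Order of examinations.** Appendix 4, footnote 4: "IOP must be measured following completion of the biomicroscopic examination". The Goldmann procedure in Appendix 5, item 3, relies on dye: "Follow the image of the fluorescein-stained semicircles while rotating the tension knob".

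**Coding and reporting.** SAP section 3.1.2 lists Staining/Erosion as a cornea item on the 0 to 3 scale. It gives a not-done level for lens status only. SAP section 4.5 makes biomicroscopy a safety endpoint. Section 6.6.2 tabulates counts and percentages of subjects or eyes with findings at each visit, and section 6 leaves missing data as they are.

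**The concern.** The routine examination cannot produce most of the grades it is meant to produce. Three of the four positive grades are defined by a dye that is normally not in the eye when the grading is done. The exception helps only if the examiner already suspects erosion, and a small focus of minimal staining is the finding least likely to raise suspicion without dye.

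Two things are at stake. First, a recorded 0 may mean either that the cornea was dyed and did not stain, or that it was not dyed. If the two are pooled, the reported frequency of staining is too low. Second, dye use is left to judgement and may differ between baseline and on-treatment visits. The study is single-arm and open-label, so baseline is the only reference, and no control group shares the same error. A shift in testing could pass for a treatment effect on the cornea, or hide one.

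**Working it through.** The documents state no figure to reproduce: they give no staining rate, no rate of dye use, and no sample size calculation (SAP section 3.3). The check is a side-by-side reading, followed by an illustration on assumed inputs.

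**1. Which grades can be given without dye?**

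| Grade | Defined by | Reachable without dye? |
|---|---|---|
| 0 | absence of erosion | yes, as worded |
| 0.5 | fluorescein staining only | no |
| 1 | fluorescein staining only | no |
| 2 | fluorescein staining only | no |
| 3 | fluorescein staining or epithelial loss | yes, by epithelial loss |

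Under the default examination only the two ends of the scale are available.

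**2. Does the tonometry dye fill the gap?** Not in the present order. Tonometry needs fluorescein at every visit, but footnote 4 puts it after biomicroscopy is complete. The dye arrives after the cornea has been graded.

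**3. What is entered for an undyed eye?** The documents do not say. SAP section 3.1.2 offers 0, 0.5, 1, 2 and 3 for the cornea. An examiner who sees no erosion can enter 0 as the scale is worded. A blank would stay missing under SAP section 6, but an entered 0 counts as an observed 0. If sites differ in this, the denominators differ as well.

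**4. Illustration (assumed inputs).** Let *p* be the true share of eyes with staining and *s* the share of those eyes that are suspected and dyed. If the other affected eyes are scored 0, the recorded share is *p* × *s*. Take 250 subjects × 2 eyes = 500 eyes and assume *p* = 10%, or 50 eyes:

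| *s* (assumed) | Eyes recorded | Recorded share |
|---|---|---|
| 0.10 | 5 | 1.0% |
| 0.25 | 12.5 | 2.5% |
| 0.50 | 25 | 5.0% |
| 0.75 | 37.5 | 7.5% |
| 1.00 | 50 | 10.0% |

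The recorded share is too low unless *s* = 1. The result simply follows the chosen *s*, so the table shows direction and not a forecast.

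**5. Baseline against follow-up.** With *p* fixed at 10%, a rise in *s* from 0.25 at baseline to 0.50 at follow-up moves the recorded share from 2.5% to 5.0% with no change in the corneas.

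**6. Would dropping undyed eyes from the denominator cure it?** Not while dye is used selectively. Let *u* be the share of unaffected eyes that are dyed. The rate among dyed eyes is *ps* / [*ps* + (1 − *p*)*u*]. This exceeds *p* whenever *s* > *u*, which is what dyeing on suspicion is meant to achieve. The error then runs upward.

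**The case against.** Read whole, the sentence in Appendix 5 describes a two-step examination: look first, then use dye where erosion is suspected. That is a coherent choice. Grade 0 speaks of erosion and not of staining, so an examiner who looks and sees none has made an assessment, if a less sensitive one. Staining is one item among several in a descriptive safety summary. Adverse events found on examination are collected separately (Protocol section 10.1, SAP section 3.7).

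Much of this stands. It rules out three stronger readings that a reader might infer:

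- **That the examination is never done with dye.** The parenthesis says otherwise.
- **That undyed eyes will be recorded as free of staining.** No text tells examiners to enter 0. The CRF is not among the documents and may have a not-done option that the SAP does not list. The supportable word is *may*.
- **That the loss can be put at a particular figure.** Any figure rests wholly on assumed values of *p* and *s*.

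The objection does not remove the mismatch itself. Permission to use dye on suspicion does not let an examiner give grades 0.5 to 2 in eyes that raise none. Adverse event reporting would not reliably catch faint staining without symptoms.

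**Conclusion.** The point holds as a mismatch between method and scale in one safety item. Low-grade staining can be scored only in eyes the examiner already suspects. The plan lists no way to separate an undyed eye from a dyed eye that did not stain. Under-recording in the per-visit table is possible, and so is a spurious change from baseline if dye use changes.

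The downward direction rests on two assumptions: that some affected eyes raise no suspicion, and that some of these are entered as 0. The size cannot be found from the documents. Severe epithelial loss can still be graded without dye. The primary endpoint, percent IOP reduction, is unaffected. The change is worth making because it is cheap and the staining frequency is otherwise hard to interpret, but it does not bear on the study's main conclusion.

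**What to change.** **Appendix 5.** Reconcile the Biomicroscopy text with the Staining/Erosion scale. Do the rest of biomicroscopy first, as now. Then grade Staining/Erosion in all eyes at every visit, baseline included, once the fluorescein for tonometry is in the eye and before the tonometer touches the cornea. Fix the timing relative to the topical anesthetic, which item 3 follows with a 4-minute wait, and keep it the same at all visits. Use the same grader where possible. Align footnote 4 of Appendix 4 with this order.

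**CRF and SAP section 3.1.2.** Add a yes/no field for fluorescein use, and code undyed eyes as not assessed for staining.

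**SAP section 6.6.2.** State the denominator for staining. If dye use stays selective, do not present a rate among dyed eyes only as the staining frequency. Report at each visit the number of eyes dyed, and the findings with and without dye.

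**Cost.** Wording, two CRF changes and a short added step at each visit; fluorescein is already needed for tonometry. The practical burden is coordination. Protocol section 8.2.3 gives biomicroscopy to the investigator or designee, while Appendix 5, item 3, gives IOP to the study coordinator or designee. The grader may have to be present at tonometry, in keeping with the same-evaluator instructions in Protocol sections 7.3 and 8.0.

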**Lids/Lashes (upper and lower)**

*Erythema*

Rating	Score	Description
None	0	Normal, without redness
Trace	+0.5	Minimal flush reddish color, confined to a small region
Mild	+1	A flush reddish color, confined to a small region
Moderate	+2	Diffused reddish color encompassing the entire lid margin
Severe	+3	Deep diffuse reddish color of lid margins and superior or inferior eye lid

*Edema*

Rating	Score	Description
None	0	Normal. No swelling of the eyelid tissue

CONFIDENTIAL

Trace	+0.5	Minimal swelling of the lids, above normal, which is regional
Mild	+1	Slight swelling of the lids, above normal, which is regional
Moderate	+2	General swelling
Severe	+3	Extensive swelling of the eyelids, with or without eversion of upper and/or lower lids

**Conjunctiva (Palpebral and Bulbar)**

*Hyperemia*

Rating	Score	Description
None	0	Normal. May appear blanched to reddish-pink without perilimbal injection. Vessels of palpebral or bulbar conjunctiva easily observed
Trace	+0.5	Minimal flush, reddish color predominantly confined to the palpebral or bulbar conjunctiva
Mild	+1	A flush, reddish color predominantly confined to the palpebral or bulbar conjunctiva
Moderate	+2	Bright red color of the palpebral or bulbar conjunctiva
Severe	+3	Deep, bright diffuse redness of the palpebral or bulbar conjunctiva

*Edema*

Rating	Score	Description
None	0	Normal. No swelling of the conjunctiva
Trace	+0.5	Minimal swelling of the conjunctiva, above normal, which is regional
Mild	+1	Mild swelling of the conjunctiva, above normal, which is regional
Moderate	+2	General swelling of the conjunctiva
Severe	+3	Extensive swelling of the conjunctiva

*Follicles*

Rating	Score	Description
None	0	No follicles
Trace	+0.5	Minimal number of elevated follicles, with minimal surrounding vasculature
Mild	+1	Few elevated follicles with minimal surrounding vasculature
Moderate	+2	Multiple elevated follicles with moderate surrounding vasculature
Severe	+3	Elevated follicles which may involve the entire conjunctiva, with engorged vasculature

**Cornea**

*Edema*

Rating	Score	Description
None	0	No edema
Trace	+0.5	Localized, minimal (trace) epithelial haze
Mild	+1	Dull glass appearance of epithelium that may include fine localized microcystic changes
Moderate	+2	Dull glass appearance of epithelium with large number of cystic changes with or without stromal edema
Severe	+3	Epithelial bullae and/or stromal edema, localized or diffuse, with or without stromal striae

*Staining/Erosion*

Rating	Score	Description
None	0	No erosion
Trace	+0.5	Minimal fluorescein staining confined to small focus
Mild	+1	Slight fluorescein staining confined to small focus
Moderate	+2	Regionally dense fluorescein staining (1 mm or greater in diameter) with underlying structure moderately visible
Severe	+3	Marked fluorescein staining or epithelial loss

**Anterior Chamber**

For the measurements of cells and flare the following settings should be used:

 
• 1x1 mm slit
 
• Highest slit lamp voltage
 
• Illumination angle of 45 degrees
 
	
 
• High magnification
 
• Low ambient lighting
 
• Same grader and slit lamp whenever possible
 

--	---

*Cells*

Rating	Score	Description
None	0	No cells seen
Trace	+0.5	1-5 cells seen
Mild	+1	6-25 cells seen
Moderate	+2	26-50 calls seen
Severe	+3	Too many cells to count

*Flare*

Rating	Score	Description
None	0	No Tyndall effect
Trace	+0.5	Tyndall effect barely discernible
Mild	+1	Tyndall beam in the anterior chamber has a mild intensity
Moderate	+2	Tyndall beam in the anterior chamber has a moderate-strong intensity
Severe	+3	Tyndall beam is very intense, and the aqueous has a white and milky appearance

**Lens Status**

Lens status will be described by the observer as phakic, pseudophakic or aphakic.

**Lens Appearance (phakic eyes only)**

Rating	Score	Description
None	0	No cataract
Trace	+0.5	Trace lens opacity
Mild	+1	Early lens opacity
Moderate	+2	Intermediate lens opacity
Severe	+3	Advanced lens opacity

### 3. Intraocular Pressure

NOTE: The examination procedure described below are to be completed for both eyes.

IOP should be measured by the study coordinator (or designee) in each eye using a Goldmann applanation tonometer affixed to a slit lamp. Measurements will be recorded on an appropriate CRF.

Please ensure tight-fitting neck wear has been loosened prior to initiating the examination. Both eyes will be tested, with the right eye preceding the left.

Instill 1 drop of topical anesthetic (eg, Ophthetic®) into each eye and wait 4 minutes before continuing with the test procedure.

#### Test Procedure:

1. With the subject seated, both he/she and the slit lamp should be adjusted so that the subject's head is firmly positioned on the chin rest and against the forehead rest without leaning forward or straining.
2. Look through the binocular viewer of the slit lamp at low power making sure the tension knob is pre-set to the low-pressure value (4-6 mmHg).
3. Follow the image of the fluorescein-stained semicircles while rotating the tension knob until the inner borders of the fluorescein rings touch each other at the midpoint of their pulsation in response to the cardiac cycle.
4. When this image is reached, remove your fingers from the tension knob and record the IOP reading along with the time of day in the CRF.

